### **3.5 Discussion of Overall Trial Design and Choice of Control Groups**

#### **3.5.1 Trial Design**

The trial has a primary objective of assessing the effect of a GnRH receptor antagonist (degarelix) on the short-term CV risk as compared to a GnRH receptor agonist (leuprolide) in patients with prostate cancer and concomitant CVD. In addition, a number of non-CV-related secondary endpoints will be studied with the purpose to further investigate the potential differences in risk-benefit profile of degarelix versus GnRH receptor agonists.

In order to minimize the risk of imbalance between the treatment arms with respect to CVD prognostic risk factors the randomization will be stratified by baseline age group (<75 and ≥75 years of age) and region (North America and Other regions).

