## 4 SELECTION OF TRIAL POPULATION

### 4.1 Trial Population

#### 4.1.1 Inclusion Criteria

Each patient must meet the following inclusion criteria before entry into the trial:

1. Signed informed consent obtained before any trial-related activity is performed.
2. Histologically confirmed adenocarcinoma of the prostate.
3. Clinical tumor staging (Tumor, Nodule and Metastasis [TNM]) available prior to treatment start; radiographic imaging (bone scan and/or CT scan and/or MRI) performed within 3 months prior to randomization. If no radiographic image is available at the time of screening, a bone scan should be performed.
4. Investigator judgment to initiate continued ADT with an intended treatment duration of 12 months or longer including any of the following disease categories:
  - A. Patients with metastatic prostate cancer at the time of diagnosis.
  - B. Patients with prostate cancer who develop metastases after local therapy.
  - C. Patients with prostate cancer with very high-risk, high-risk or intermediate-risk disease with features of unfavourable prognosis who are going to be treated with definitive radiation therapy in combination with at least 12 months of neoadjuvant/adjuvant ADT.
  - D. Patients with biochemical recurrence after local therapy who have a PSA doubling time <12 months.
  - E. Patients previously treated with definitive local therapy (without ADT combination) who due to risk features such as positive margins, seminal vesicle invasion, extracapsular extension, or detectable PSA, will be treated with salvage radiation therapy in combination with neoadjuvant/adjuvant ADT that is planned for 12 months or longer.
  - F. Patients with locally advanced prostate cancer who are not candidates (who are unsuited) for definitive therapy with surgery or radiation and will be treated with primary ADT.
5. Patients must be treatment-naïve with regard to ADT at time of randomization (with the exception of prior history of neoadjuvant/adjuvant ADT to definitive therapy for which the last administration, e.g., injection of a depot ADT formulation was at least 12 months prior to randomization).
6. Patients must have a screening serum testosterone level above the lower limit of normal range, defined as >150 ng/dL (5.2 nmol/L), apart from those who had prior neoadjuvant/adjuvant ADT (>12 months prior to randomization) where non-castrate range (>50 ng/dL or  $\geq 1.73$  nmol/L) should be applied.

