### 7.3.4 Histology, Treatment History (or Previous Therapy), Stage of Prostate Cancer and Eastern Cooperative Oncology Group (ECOG) Score

The date of diagnosis of prostate cancer, stage of prostate cancer, and information on previous prostate cancer therapy will be recorded in the eCRF at the Screening visit. Moreover, the ECOG performance status will be assessed for eligibility.

Stage of the patient's prostate cancer prior to randomization will be based on clinical assessment and radiographic imaging (e.g. bone scan, MRI or CT performed as per standard clinical practice at

the discretion of the Investigator). Radiographic imaging should be performed within 3 months prior to randomization, and will be classified according to the TNM classification. In case no radiographic image is available prior to screening, a bone scan will be performed as part of the screening procedures. The TNM staging data must be available for trial documentation before randomization. The TNM stage both at the time of prostate cancer diagnosis and at the time of the Screening visit of this trial will be recorded.

For patients having undergone radical prostatectomy, pre-treatment TNM stage will be recorded.

Histology of the prostate cancer will be reported using Gleason grading. An appropriate Gleason grade for each of the two most predominant patterns will be recorded.

The ECOG performance status will be assessed according to the following scale ([Oken, 1982](#)):

- 0 Fully active, able to carry on all pre-disease performance without restriction.
- 1 Restricted in physically strenuous activity but ambulatory and able to carry out work of a light or sedentary nature, e.g., light house work, office work.
- 2 Ambulatory and capable of all self-care but unable to carry out any work activities. Up and about more than 50% of waking hours.
- 3 Capable of only limited self-care, confined to bed or chair more than 50% of waking hours.
- 4 Completely disabled. Cannot carry on any self-care. Totally confined to bed or chair.

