3.2 Determination of Sample Size

The primary objective is to assess the effect of degarelix on the risk of MACEs (a composite of death due to any cause, non-fatal myocardial infarction or non-fatal stroke) occurring during a 1-year period as compared to treatment with leuprolide in patients with prostate cancer and concomitant CVD.

The observed one-year event rates for primary MACE endpoint are 5.3% and 12.1% for degarelix and LHRH agonist, respectively, in the global patient population with prior CVD were derived from a post-hoc analysis of degarelix safety data. This would correspond to an unadjusted treatment-

Date: 24 Feb 2021 E-Statistical Analysis Plan-19595; Ver.7.0 Supersedes: 6.0 Page 14 of 51

related hazard ratio of 0.42. (In comparison, the adjusted hazard ratio is 0.39 (95% confidence interval [CI] = [0.21; 0.71]).) Furthermore, based upon the re-assessment of the potential CV events captured in the degarelix safety data by an independent cardiologist, the one-year event probability for CV event or death due to any cause are 4.8% and 9.3% for degarelix and leuprolide respectively. This corresponds to an unadjusted hazard ratio of 0.50 (in comparison, the adjusted hazard ratio is 0.48 (95% confidence interval is [0.23,0.87]). Accounting for the uncertainty in the post-hoc analysis of the global pooled data and the re-assessment of the potential CV events by a single independent cardiologist, the one-year event rates for sample size calculations are set to 5.1% and 10.2% for degarelix and leuprolide, respectively. This corresponds to a hypothesized hazard ratio of 0.49.

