3.2.1 Fixed Trial Design

Given the alternative hypothesis, a power of 80% and a signficiance level of 5%, the expected number of events required at the final analysis is 61. The sample size required for achieving this number of events assumes that all patients are followed-up for primary outcome (MACEs) for 12 months (28 days each) after start of treatment and an annual drop-out rate of 5%. Assuming these characteristics a total sample size of 811 patients is required.

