3.2.3 Adjustments for Sample Size Re-Estimation

The conditional power for different sample size increases will be evaluated at the interims using SAS. In case of a sample size increase, the final test statistic is adjusted by using the normal inverse method in order to protect the two-sided Type I error rate at 5%.

The sample size calculations are performed with ADDPLAN™ 6, licensed by ADDPLAN, Inc., an Aptiv Solutions company and presented in Table 1.

Page 15 of 51

Table 1 Sample Size Calculations (Number of Events Rounded Upwards)

Information Rate	Stop for futili	ty/No eviden	ce reject H ₀	Successful trial (Reject H ₀₎	g gnant	Power	Events
	Test Statistic	Hazard Ratio	Conditional Power	Test Statistic	α spent		
50%	≤ 0.7	≥0.78	≤8.5%	-	< 0.0001	-	33
100%	≤1.96	≥0.61	-	≥ 1.96	0.025	80%	66

- Assuming constant hazards, $\lambda_{degarelix} = 0.0523/year$ $\lambda_{leuprolide} = 0.1076/year$
- 5% drop out rate in each arm
- 1:1 randomization ratio

When d, the number of events, has been observed, the approximate relationship between the standardized test statistic, Z, and the hazard ratio (HR) as given in (Jennison and Turnbull, 2000) is,

$$Z \approx log(HR^{-1})\sqrt{d/4}$$

For reasons of interpretation, both Z and the hazard ratio are reported in design tables.

Date: 24 Feb 2021 E-Statistical Analysis Plan-19595; Ver.7.0 Supersedes: 6.0 Page 16 of 51

4 Patient Disposition

All patients screened and randomized will be accounted for. All post-randomization discontinuations will be summarized by time of, and reason for, discontinuation. The number of patients screened and not randomized will be presented with the reason(s) for screen failure.

Special attention should be paid to those patients who discontinue treatment with investigational medicinal product (IMP) and start an alternative treatment during the trial, including the dates corresponding to going off the randomized drug, i.e. the date of the last injection and the start of a new treatment, i.e. the date the new treatment was initiated.

In addition, the breakdown of the overall disposition of patients by age group (<75 years of age, ≥75 years of age) and region following the design (stratification) of the trial will be provided. Also, the number of patients screened and randomized, overall and by age group (<75 years of age, ≥75 years of age) and region will be provided.

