9.3.6 Time from Randomization to Failure in Progression-Free Survival

Progression-free survival (PFS) is a composite endpoint consisting of the following conditions:

- Death
- Radiographic disease progression defined as one or more new metastatic skeletal lesions observed on bone scan; one or more new metastatic extra-skeletal lesions at least 1.5 cm in greatest dimension visible on computed tomography or magnetic resonance imaging scan as confirmed by the Investigator.
- Introduction of additional therapy related to prostate cancer treatment including radiation, anti-androgens and second-line treatment. (ATC and MedDRA codes for disease progression are included in Appendix 3)
- PSA failure defined as the time from randomization to the second occasion (must be at least two weeks apart from the first and correspond to consecutive measurements) in which the PSA value fulfills the following criteria:
 - I. An absolute increase of ≥ 5 ng/ml above nadir and
 - II. An increase of > 50 % of nadir

Time to PFS failure is therefore defined as the time, measured in days, from randomization to the first occurrence of one of the above composite endpoint criteria. Patients discontinuing from treatment/withdrawn from the study will be censored at the time of discontinuation/withdrawal. Time to PFS failure will be analyzed using the Kaplan-Meier estimator of the survival function, the Cox regression model for the hazard rate and the log-rank test of the null hypothesis of equal hazard functions, stratified by age group and region. The p-value of the two-sided stratified log-rank test with significance level of 5% will be presented along with plots of the estimated survival functions for the two treatment groups, stratified by age group and region. The estimated hazard ratio and the associated 95% confidence interval and p-value comparing the treatment with Degarelix to Leuprolide will also be presented.

TLF Table: Secondary Endpoint: Time to PFS Failure - FAS

TLF Figure: Survivor Function for Time to PFS Failure - FAS

Page 30 of 51

9.3.7 Testosterone levels at day 28, 168 and 336 in patients treated with degarelix and leuprolide

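### The PFS comparison is stratified by age group and region only; adding the recorded screening cancer stage would recover some precision and correct for chance stage imbalance

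*SAP*

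**What the plan says.** - **Population.** Criterion 4 (Protocol 4.1.1) admits, under 4A, "Patients with metastatic prostate cancer at the time of diagnosis", and under 4B metastases that appear after local therapy. It also admits intermediate- to very-high-risk disease going to definitive radiation (4C), biochemical recurrence (4D), salvage radiation (4E) and locally advanced disease unsuited to definitive therapy (4F).
- **Randomization.** The strata are age group and region (Protocol 4.2.2). Protocol 3.5.1 gives the reason: "In order to minimize the risk of imbalance between the treatment arms with respect to CVD prognostic risk factors the randomization will be stratified".
- **PFS analysis.** SAP 9.3.6 uses Kaplan-Meier, a Cox model and a "log-rank test of the null hypothesis of equal hazard functions, stratified by age group and region". Protocol 9.6.3.7 names no strata for PFS; the general rule in Protocol 9.6.1 supplies the same two.
- **Covariates.** The only prespecified covariates are cardiovascular risk factors. Protocol 9.6.1 assigns them to the MACE models, and SAP 9.3.1, 9.3.4 and 9.3.5 bring them into the Cox models for the CV composite, all-cause death and CV death where suitable. SAP 9.3.6 has none.
- **Stage data.** Protocol 7.3.4: "The TNM stage both at the time of prostate cancer diagnosis and at the time of the Screening visit of this trial will be recorded". SAP 7.1.3 groups stage as localised, locally advanced, metastatic or not classifiable, for a baseline summary by treatment group.
- **Status.** PFS is an other secondary endpoint without multiplicity control (SAP 9.3).

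**The concern.** PFS is a cancer endpoint: new metastases, PSA failure, added cancer therapy or death. The two strata in its analysis were chosen for cardiovascular prognosis. Disease stage, which plausibly separates patients with very different PFS risk, is neither balanced at randomization nor used in the comparison.

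There are two consequences. First, pooling patients with different failure rates in one risk set pulls the hazard ratio toward 1 and costs power. Second, if one arm happens to receive more metastatic patients, the difference passes into the PFS hazard ratio. The baseline table would show the imbalance, but nothing visible in the plan would correct it.

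**Working it through.** **1. The plan's own figures.** The documents size the trial for MACE only. SAP 3.2 states: "This corresponds to a hypothesized hazard ratio of 0.49". The hazards in SAP Table 1 give 0.0523/0.1076 = 0.486. With 80% power, two-sided 5% and a "1:1 randomization ratio", the Schoenfeld formula gives

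events = 4 × (1.960 + 0.842)² / (ln 0.486)² = 60.3, rounded up to 61, as SAP 3.2.1 states.

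With 5% annual dropout and one full year of follow-up, the sample sizes come to 818 (plan: 811) and, for 66 events, 885 (plan: 876), both within 3%. (Using 336 days with the same annual hazards gives about 884 and 957; that is a separate matter.) No power, event rate or effect size is given for PFS, so there is no PFS figure to reproduce.

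**2. Size of a chance imbalance.** Inputs: 545 randomized (SAP 3); metastatic share p of 20% to 40% (assumed). The standard deviation of the between-arm difference in share is √(p(1−p) × 4/545), and the 95% range is ±1.96 times that. If metastatic patients have k times the hazard of the rest, a difference d between arms alone multiplies the hazard ratio by about

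[1 + (k−1)(p + d/2)] / [1 + (k−1)(p − d/2)], or its reciprocal if the imbalance runs the other way.

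| p | SD (points) | 95% range (points) | k = 2 | k = 4 | k = 8 |
|---|---|---|---|---|---|
| 0.2 | 3.4 | ±6.7 | 1.06 | 1.13 | 1.22 |
| 0.3 | 3.9 | ±7.7 | 1.06 | 1.13 | 1.19 |
| 0.4 | 4.2 | ±8.2 | 1.06 | 1.12 | 1.16 |

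Example: p = 0.3, d = 0.077, k = 4 gives (1 + 3 × 0.3385)/(1 + 3 × 0.2615) = 2.0155/1.7845 = 1.13.

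**3. Power, three stage groups.** Simulated stratified log-rank tests: 545 patients, 1:1, 336 days, 5% annual dropout, 4,000 runs per scenario. Region is left out because its mix is not given. Stage mixes are 50/25/25 and 40/30/30 (localised/locally advanced/metastatic). Treatment effects are HR 0.5 with 15% control failure and HR 0.6 with 30%. All are assumed. The example column is HR 0.6 with the 50/25/25 mix.

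| Stage hazards | Example power, without → with stage | Gain over all four settings |
|---|---|---|
| 1 / 1.5 / 2 | 80.5% → 81.2% | 0 to 1 point |
| 1 / 2 / 4 | 79.4% → 82.7% | 1 to 3 points |
| 1 / 3 / 8 | 73.8% → 82.3% | 3 to 9 points |

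**4. Power, two stage groups.** 545 patients, 336 days, 5% annual dropout, 30% metastatic, HR 0.60, one-year control failure 10% in non-metastatic patients (assumed).
- Metastatic failure 45%, a hazard multiple of ln 0.55/ln 0.90 = 5.7: power 57% → 64%.
- Metastatic failure 60%, a multiple of ln 0.40/ln 0.90 = 8.7: power 62% → 75%, a gain of 13 points.

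**5. Type I error.** In the step 3 scenarios with no treatment effect, rejection without stage is 4.2% to 5.4%. In the tenth of runs with the largest metastatic imbalance it is about 5% to 10.5% without stage and 4% to 6% with it. Each of those subsets has about 400 runs, so the simulation standard error near 5% is √(0.05 × 0.95/400) = 1.1 points.

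**The case against.** The strongest reply is that this is an efficiency preference and not an error. SAP 9.3.6 analyses by the factors used at randomization, as Protocol 9.6.1 requires. A reader might infer that the PFS test is invalid, or that nothing protects it from stage imbalance. The documents do not support that: randomization protects the comparison on average, the p-value allows for chance imbalance, and step 5 shows type I error close to 5%. What remains is lost precision, and error conditional on the imbalance that actually occurs.

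Second, power for PFS was never promised. The objective is to evaluate PFS failure rates, the trial was sized for MACE, and it stopped early. This limits the importance of the point, but the plan still prescribes a two-sided 5% test and a hazard ratio for PFS.

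Third, the larger gains need strong prognosis. With a 2-fold stage hazard the gain is at most about 1 point. This stands. No scenario showed a meaningful loss from adding stage.

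Fourth, added radiation counts as PFS failure (SAP 9.3.6, with radiotherapy codes in Appendix 3), while 4C and 4E enrol patients with radiation planned, and no exclusion for planned radiation is visible. Non-metastatic patients could therefore fail by definition, so it cannot be assumed that metastatic patients fail sooner. Scheduled bone scans only at the end visits and roughly quarterly PSA also make exponential failure times a simplification. Stratification works whichever way stage predicts, but the simulated sizes are less certain.

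Fifth, a reader might assume the stage variable already exists in the needed form. SAP 7.1.3 does not say whether it uses TNM at diagnosis or at screening, so a short derivation is needed. Finally, text at the end of SAP 9.1 is missing from the public copy and might define covariates; SAP 9.3.6 refers to none.

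**Conclusion.** The point holds as a low-cost improvement to a secondary analysis. The plan records stage at screening, admits a population that varies widely in stage, and leaves stage out of its one time-to-event comparison built on cancer progression.

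Under assumed stage mix, PFS rates and treatment effect, the power forgone is about 0 to 1 point with a roughly 2-fold stage hazard and up to about 9 to 13 points with a roughly 8-fold one. A 95%-edge imbalance moves the hazard ratio by a factor of about 1.06 to 1.22. No single loss figure can be given, because the documents supply none of these inputs. The primary MACE result and the fixed testing sequence are not touched.

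**What to change.** In SAP 9.3.6:

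- Add metastatic status (M1 versus not M1 or not classifiable) as a stratification factor in the PFS log-rank test and Cox model, alongside age group and region. Keep the two-factor version as a sensitivity analysis.
- State that the variable uses the screening TNM and not the diagnosis TNM, so that 4B patients are classed by their stage at entry.
- Reconcile counting radiation as PFS failure with the radiation planned under 4C and 4E. Consider the criterion 4 category as an alternative or additional stratum.
- Make the change before PFS is compared by arm, so that the choice cannot depend on the result.

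The cost is one short derivation and somewhat smaller strata (at most 2 × 2 × 2 = 8). No new data are needed, and the testing hierarchy stays as it is.

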9.3.8 Total number of Cardiovascular-Related Hospitalizations over the duration of the trial

The total number of CV-related hospitalizations over the duration of the trial is defined as the number of hospitalizations due to CV-related adverse events, observed during the 12 month follow-up period for each patient.

The number of CV-related hospitalizations will be analyzed using a negative binomial model. The dependent variable will be the number of CV-related hospitalizations. The model will include a factor variable for treatment, the baseline count of CV-related hospitalizations (if available) as a covariate and will be further adjusted by including the logarithm of the number of days of follow-up for each patient as an offset. The inclusion of the offset term systematically adjusts the estimate of the treatment effect for potential differences in the duration of follow-up between patients. The model will further be adjusted for age-group and region. The estimated treatment difference with a 95% confidence interval will be presented.

TLF Table: Secondary Endpoint: Number of CV-related hospitalizations over the duration of the trial – FAS

9.3.9 Total number of Coronary Artery By-Pass Grafting or Percutaneous Coronary Intervention Procedures over the duration of the trial

The total number of CABG or PCI procedures observed over the duration of the trial will be analyzed in the same manner as the total number of CV-related hospitalizations, outlined in Section 9.3.8.

TLF Table: Secondary Endpoint: Number of CABG or PCI over the duration of the trial – FAS

Page 31 of 51

9.3.10 Total number of Cardiovascular-Related Emergency Room Visit Events Observed over the duration of the trial

The total number of CV-related ER visit events observed over the duration of the trial for each patient will be analyzed in the same manner as the total number of CV-related hospitalizations, outlined in Section 9.3.8.

TLF Table: Secondary Endpoint: Number of Cardiovascular-related emergency room visits over the duration of the trial – FAS

9.3.11 Difference in Quality Adjusted Life Year (QALY) During One Year of Treatment

The EQ-5D-5L questionnaire can be used to estimate the QALY. The QALY is a measure of the value of health outcomes. Since health is a function of length of life and QoL, the QALY was developed as an attempt to combine the value of these attributes into a single index number. The basic idea underlying the QALY is simple: it assumes that a year of life lived in perfect health is worth 1 QALY (1 Year of Life × 1 Utility value = 1 QALY) and that a year of life lived in a state of less than this perfect health is worth less than 1. The QALY is derived as a cumulative measure for the treatment duration as the AUC of the time versus the index value. The AUC will be calculated using the trapezoidal rule for each of the visits values in relation to the baseline.

A detailed derivation of the QALY:

- The EQ-5D-5L health state is converted into a single index value. The index values are country specific and we will use the value sets for the USA (http://www.euroqol.org/home.html.).
- 2) The QALY at the end of the trial is derived as the cumulative AUC for the index value as a function of time during the 12 months of treatment. This will be calculated as:

$$AUC = \sum_{i=1}^{i} \left(\frac{index_{(i-1)} + index_i}{2} \right) \times Time_{(i-(i-1))}$$

Where i=1, 2 and 3 for the corresponding visits at month 6, 11 and 12. The value, i=0, corresponds to baseline.

Time is measured as the actual number of days from baseline date of EQ-5D to each of the post-baseline EQ-5D Questionnaire completion dates during the 12 month trial.

The QALY at Visit 13 will be calculated for any patients who have a non-missing baseline index value. That is, any patients who are missing the EQ5D index value at baseline will not have a QALY measurement. Last observation carried forward principle will be used for missing measurements at Visit 8 or Visit 13 using only post-baseline values. The EQ5D index value will be carried forward to the planned visit date in order to calculate the QALY at 12 months. For patients with missing index value at Visit 8, but with known index value either at Visit 13 or 14, the QALY will be calculated as the AUC from baseline up to the next known visit.

The mean QALY at the end of the trial (12 months [1 month=28 days]) will be summarized by treatment arm and compared using an analysis of covariance (ANCOVA) model, where the QALY is the dependent variable and adjusted for treatment, age-group and region respectively.

9.3.12 Change from Baseline in Mean Total and QoL International Prostate Symptom Score during One Year of Treatment

The severity of lower urinary tract symptoms (LUTS) will be investigated using the total IPSS score. IPSS is a questionnaire containing eight questions regarding incomplete emptying, frequency, intermittency, urgency, weak stream, straining and nocturia and one question relating to the quality of life. Each question is assigned a total score on a scale from 0 to 5. The total IPSS score is then calculated as the summation over the responses for question 1 to 7.

The eighth question regarding QoL is in relation to urinary symptoms denoted IPSS-QoL. The response to this question is analyzed separately and not included in the IPSS total score.

Missing values will not be imputed for this endpoint. If responses are missing to one or more of questions 1-7, the IPSS total score is considered missing as well. Results will be presented based on the observed cases.

Changes from baseline in the IPSS total score and QoL score will be compared between treatments longitudinally using repeated measures analysis of covariance (ANCOVA) with the change from baseline as the dependent variable and the baseline score as a covariate, treatment, age-group, region and visit as factors, including treatment by visit interaction term, assuming the working correlation matrix has the unstructured form implemented in SAS PROC MIXED. Based on the repeated measures ANCOVA model, the two-sided 95% confidence limits of the adjusted treatment contrasts and associated p-values will be provided.

TLF Table: Secondary Endpoint: IPSS - FAS

9.3.13 Change from Baseline in the Mean Duke Activity Status Index and Cardiac Anxiety Questionnaire Score during One Year of Treatment

The DASI and CAQ will be assessed at baseline (Visit 2), Visit 8, 14 and at the End-of-Trial visit. The change from baseline in DASI total score as well as CAQ total and domain scores will be compared between treatments longitudinally using repeated measures ANCOVA with the change from baseline as the dependent variable and the baseline score as a covariate, treatment, age-group, region and visit as factors, including treatment by visit interaction term, assuming the working correlation matrix has the unstructured form implemented in SAS PROC MIXED. Based on the ANCOVA model, the two-sided 95% confidence limits of the adjusted treatment contrasts and associated p-values will be provided.

TLF Table: Secondary Endpoint: The change in the mean DASI Score during one-year of treatment-FAS

Page 33 of 51

TLF Table: Secondary Endpoint: The change from baseline in the mean CAQ Score during one-year of treatment – FAS

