#### 7.2.3.2 EQ-5D-5L

The EQ-5D-5L will be assessed at baseline (Visit 2), at Visit 8 and at the End-of-Trial visit.

EQ-5D-5L is a standardized measure of health status developed in order to provide a simple, generic measure of health for clinical and economic appraisal (<http://www.euroqol.org/home.html>). EQ-5D-5L essentially consists of 2 systems - the EQ-5D-5L descriptive system and the EQ visual analogue scale (EQ VAS). The EQ-5D-5L descriptive system comprises the following 5 dimensions: mobility, self-care, usual activities, pain/discomfort and anxiety/depression. The EQ VAS is an overall estimation of the present health status. An EQ-5D-5L health status estimation

may be converted to a single summary index by applying a formula that essentially attaches weights to each of the levels in each dimension. This formula is based on the valuation of EQ-5D-5L health status from general population samples in each country. Conversion from EQ-5D-5L into Quality Adjusted Life Year (QALY) units will create data for pharmacoeconomic evaluations of degarelix, as described in Section 9.6.3.13.

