### **9.6.3.13 Quality Adjusted Life Year**

The EQ-5D-5L questionnaire can be used to estimate the QALY. The QALY is a measure of the value of health outcomes. Since health is a function of length of life and QoL, the QALY was developed as an attempt to combine the value of these attributes into a single index number. The basic idea underlying the QALY is simple: it assumes that a year of life lived in perfect health is worth 1 QALY (1 Year of Life  $\times$  1 Utility value = 1 QALY) and that a year of life lived in a state of less than this perfect health is worth less than 1. The QALY is derived as a cumulative measure for the treatment duration as the AUC of the time versus the index value. The AUC will be calculated using the trapezoidal rule for each of the visits values in relation to the baseline.

The mean QALY at the end of the trial (12 months [1 month=28 days]) will be summarized by treatment arm and compared using an ANCOVA model, where the QALY is the dependent variable with treatment as the comparison factor, respectively.

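### SAP 9.3.11 builds the QALY from time in days with no conversion to years, so the reported figures would be utility-days, not QALYs

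*SAP*

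**What the plan says.** SAP 9.3.11 fixes the scale first: "1 Year of Life × 1 Utility value = 1 QALY". Protocol 9.6.3.13 gives the same anchor: "it assumes that a year of life lived in perfect health is worth 1 QALY".

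Step 2 of the SAP's detailed derivation then equates the QALY with the area: "The QALY at the end of the trial is derived as the cumulative AUC for the index value as a function of time". The formula sums the mean of two adjacent index values times a Time term, and the SAP defines that term in days: "Time is measured as the actual number of days from baseline date of EQ-5D to each of the post-baseline EQ-5D Questionnaire completion dates". Neither document gives a divisor.

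For missing late assessments the SAP uses a planned date instead of an actual one: "The EQ5D index value will be carried forward to the planned visit date in order to calculate the QALY at 12 months". The resulting value goes into an ANCOVA with treatment, age group and region, and no term for the length of time integrated.

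**The concern.** The definition and the derivation in the same section use different units. The definition is per year; the derivation is in days. A programmer who follows the derivation produces a variable labelled QALY that is several hundred times too large for that label.

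The scale matters because of the use the protocol names. Protocol 7.2.3.2 says that the conversion to QALY units is meant to supply data for pharmacoeconomic evaluation of degarelix. That use depends on the size of the estimate and not on its p-value.

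A second, smaller matter is the end point of the integration. Patients with an observed final questionnaire are integrated to the date they completed it, and carried-forward patients to the planned date. Two patients with the same health can therefore receive different 12-month values.

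**Working it through.** **Inputs**

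- Scale: 1 QALY = 1 year at utility 1 (SAP 9.3.11, Protocol 9.6.3.13).
- Time unit: days (SAP 9.3.11, step 2).
- Assessments: "Where i=1, 2 and 3 for the corresponding visits at month 6, 11 and 12" in the SAP. With the days in Protocol Table 1, these are Days 168, 308 and 336 after baseline. Protocol 7.2.3.2 lists baseline, Visit 8 and End-of-Trial only, which gives Days 0, 168 and 336.
- Visit window: ±7 days (Protocol Table 1), so Visit 14 falls on Day 329 to 343.
- Year length: not stated for the QALY. Assumed here to be 365.25 days, with 365 and 336 as alternatives.

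**1. The plan's own anchor.** One calendar year at utility 1 should return 1. The rule gives (1 + 1)/2 × 365.25 = 365.25. The anchor is not reproduced.

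**2. Perfect health over the trial.**

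- SAP visits: 168 + 140 + 28 = 336.
- Protocol visits: 168 + 168 = 336.

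The Month 11 term makes no difference here.

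**3. After conversion.**

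- Divisor 365.25: 336/365.25 = 0.920.
- Divisor 365: 336/365 = 0.921.
- Divisor 336: 336/336 = 1.00.

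The choice between 365.25 and 336 changes every mean, difference and confidence limit by a factor of 365.25/336 = 1.087.

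**4. A treatment difference.** Take, for illustration, a utility difference of 0.02 held for 336 days. As written it is reported as 0.02 × 336 = 6.72. Divided by 365.25 it is 0.018 QALY; divided by 336 it is 0.020.

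**5. The test.** Dividing the outcome by a constant c divides both the treatment coefficient and its standard error by c, so their ratio and the p-value stay the same. An ANCOVA on 545 simulated patients confirmed this: the estimates were 3.246 and 0.00889 (ratio 365.25), with p = 0.459 both times.

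**6. The Time term.** The SAP's sentence describes days from baseline to each questionnaire, while the formula's subscript implies the interval between consecutive visits. Steps 1 to 5 use the interval. If days from baseline were put into every term, perfect health would give 168 + 308 + 336 = 812. The wording therefore needs correcting as well as the unit.

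**7. The end point.** At a constant utility of 0.8:

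| Last assessment | Area (utility-days) | Divided by 365.25 |
|---|---|---|
| Day 329 | 263.2 | 0.721 |
| Day 336 | 268.8 | 0.736 |
| Day 343 | 274.4 | 0.751 |

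Relative to Day 336 the change is 7/336 = 2.1% either way. The full spread between the two extremes is 11.2 utility-days, or 0.031 QALY.

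**The case against.** The strongest reply is that the section plainly intends QALY units. The anchor stands a few lines above the formula, and Protocol 7.2.3.2 speaks of converting into QALY units. On that view days are only how the interval is measured, and any programmer would divide. A mean in the hundreds would be noticed, one division recovers the right figure, and no test changes. The output shells might state the unit, but SAP Section 14 places their overview in a separate document, so this cannot be checked.

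Much of this stands: the error is recoverable and leaves the inference alone. It does not settle the matter, because the documents support two divisors. They anchor the QALY to a year of life, yet the protocol's Duration of Treatment section calls 336 days one year, and SAP 9.3.11 reports the QALY at 12 months of 28 days. For the same reason, a reader who infers that 0.92 is the documents' own value for perfect health goes too far: it rests on a calendar year that neither document states for this endpoint.

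On the end point, the reply is that integrating to the actual date is legitimate, that the same window applies to both arms, and that the planned date is the centre of the window. That also stands. A reader might take the 0.031 QALY spread as a possible bias in the treatment comparison. It compares two individuals at opposite ends of the window, and nothing in the documents suggests that visit timing differs by arm.

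**Conclusion.** The derivation is wrong as written. It gives 336 for perfect health over the trial, against 0.92 with a calendar-year divisor or 1.00 with the trial's 336-day year. The means, the treatment difference and the confidence limits carry the same factor of 365.25 or 336; the p-value does not. These figures take Time as the interval between assessments, as the formula's subscript implies.

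The varying end point is real but secondary. It adds timing noise of up to about 2% per patient, which rescaling does not remove and for which the ANCOVA has no term. By contrast, SAP 9.3.8 uses a log-days offset for hospitalization counts.

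The stakes are limited. The QALY comparison is a secondary analysis without multiplicity control (SAP 9.3), so the point concerns what is reported and its economic use, not the trial's conclusion on its primary endpoint.

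**What to change.** In step 2 of SAP 9.3.11:

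- Define Time as the number of days between consecutive EQ-5D assessments.
- Divide the area by a named year length. A divisor of 365.25 matches the year-of-life anchor, and the SAP should then state that the maximum over 336 days is 0.92. If the trial's 336-day year is intended, state that and give the maximum as 1.00.
- As a lesser improvement, integrate every surviving patient to Day 336: interpolate when the last assessment is later, and carry forward when it is earlier.

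The first two changes take one or two sentences and a small code change, with no new data. The visible cost is that the reported QALYs look smaller. Before the common end point can be programmed, the SAP must settle which visits enter the sum, because it uses Month 11 and Visit 13 while the protocol says: "The EQ-5D-5L will be assessed at baseline (Visit 2), at Visit 8 and at the End-of-Trial visit". How deaths enter the QALY is a separate question that this change does not answer.
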